### 4.2 INCLUSION CRITERIA

The patient population that will be included in the NIS must fulfill all the following criteria:

- I 01. Signed informed consent for prospective patients. No need for signed informed consent for retrospective patients (waiver).
- I 02. Male or female aged 18 years or above for prospective patients. No age restriction for retrospective patients.
- I 03. Histological diagnosis of MTC (for retrospective patients [prevalent MTC patients] diagnosis could be as early as possible, without any limitation for the date of diagnosis).
- I 04. Patients with symptomatic and aggressive sporadic MTC, who have unresectable, locally advanced/metastatic disease. (The factors considered by the Investigator to determine a patient's disease to be symptomatic and aggressive will be recorded in the electronic case report form [eCRF], allowing for missing data for the retrospective patients).
- I 05. Measurable disease:
  - Assessment confirmed within the 12 weeks previous to start of treatment, and
  - Defined according to RECIST 1.1: at least 1 lesion, not irradiated, that can be accurately measured as  $\geq 10$  mm in the longest diameter (except lymph nodes which must have short axis  $\geq 15$  mm) with computed tomography (CT) or magnetic resonance imaging (MRI) and which is suitable for accurate repeated measurements. Measurable lesions with calcifications should not be assessed as target lesions unless no other measurable lesion is available.

Known definite RET mutation status (definition according to [Section 3.2](#)). The status should be:

- For prospective patients prescribed with vandetanib: positive or negative.
- For prospective patients not prescribed with vandetanib: negative.
- For retrospective patients prescribed or not prescribed with vandetanib: negative.

- For prospective patients: RET mutation status must be determined from a tumor sample obtained within 18 months prior to enrollment. It is strongly recommended that a tissue sample obtained within 6 months prior to enrollment is used. For retrospective patients: RET mutation negative mutation status could have been determined within 18 months before or after start of treatment (with vandetanib or another drug). In case of retrospective patient treated with another drug, the patient should have been treated with vandetanib at any time.

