## **5 WITHDRAWAL OF PATIENTS**

### **5.1 CRITERIA FOR WITHDRAWAL**

Patients may be withdrawn from the NIS at any time. Specific reasons for withdrawing a patient from this NIS are:

1. Voluntary withdrawal by the patient who is at any time free to withdraw his/her participation in the NIS, without prejudice to further treatment (not applicable for retrospective patients).
2. Incorrect enrollment (inclusion/exclusion criteria are not fulfilled).
3. Inclusion in a clinical trial at any time during the study (not applicable for retrospective patients).

Discontinuation of the patient treatment is not a criterion for withdrawal from the study. In this case, the patient can continue in the study, until death, loss to follow-up, or end of study.

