### **5.2 PROCEDURES FOR WITHDRAWAL**

For prospective patients: patients who withdraw should be asked about the reason(s) for their withdrawal. No specific procedures after withdrawal are required per study but continuation of patient assessment and treatment according to routine clinical practice.

No further data will be collected on prospective patients following withdrawal from the study.

Prospective patients who were not included (eg, for restrictive inclusion/exclusion criteria) or withdrawn from the study (eg, withdrawn due to AE but continuation of assessment and treatment according to routine practice) will still be considered for the retrospective data collection: if they meet the inclusion criteria for the retrospective data collection, the same patient ID will be used in the study database and the patient will be classified as retrospective patient for data analyses.

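### Section 5.2 moves validly enrolled prospective patients who later withdraw into the retrospective cohort for analysis, so cohort depends on a post-enrolment event and only RET-negative withdrawals can be recovered

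*Protocol*

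**What the plan says.** Protocol section 5.2 (Procedures for withdrawal) makes two statements in sequence. The first is unqualified: "No further data will be collected on prospective patients following withdrawal from the study". The second covers prospective patients who were never included and those who were included and then withdrew. Its example of the latter is a patient "withdrawn due to AE but continuation of assessment and treatment according to routine practice". Both kinds may re-enter on condition that they satisfy the retrospective entry criteria, and they keep their existing identifier. On the analysis the rule is explicit: "the patient will be classified as retrospective patient for data analyses".

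Section 5.1 (Criteria for withdrawal) lists three specific reasons: voluntary withdrawal ("Voluntary withdrawal by the patient who is at any time free to withdraw his/her participation in the NIS"), incorrect enrolment, and entry into a clinical trial. The first and third do not apply to retrospective patients. An adverse event is not listed, and the section adds: "Discontinuation of the patient treatment is not a criterion for withdrawal from the study".

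Section 4.2 (Inclusion criteria) sets the RET status allowed in each part. The line on prospective vandetanib patients reads "For prospective patients prescribed with vandetanib: positive or negative". The line that governs the retrospective part is narrower and leaves no place for RET-positive patients: "For retrospective patients prescribed or not prescribed with vandetanib: negative".

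Section 13.3 reports every analysis by source group and pooled, within each RET status, and gives confirmation of comparability as the purpose of the source-group columns.

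**The concern.** A patient's analysis cohort should be fixed by how the patient entered the study. Here a patient who consented, was enrolled correctly and was followed prospectively changes cohort because of a later event. The one example given, an adverse event, is close to an outcome the study reports: objective E in section 2 includes adverse events leading to discontinuation of vandetanib.

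Two things are at stake. The first is the side-by-side reading of prospective and retrospective RET-negative patients, which supports pooling them. The second is the contrast between RET groups. One group has a route by which outcomes after withdrawal re-enter the dataset, and the other does not.

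There is also a conduct problem. Sites cannot tell from section 5.2 whether to stop or continue collecting data after withdrawal, or whether a patient who withdrew voluntarily may be taken back in under the consent waiver of section 10.2.

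**Working it through.** **Plan's own figures.** The protocol gives no figure for this rule. Its only computed design figure is Table 1, which reproduces: 35% ± 1.96 × 0.4770/√n gives 14.1–55.9% (n = 20), 16.3–53.7% (n = 25) and 17.9–52.1% (n = 30). Nothing below disputes it.

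**Who can be reclassified.** The condition in 5.2 is that the patient meets the retrospective inclusion criteria.

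- RET-negative, withdrawn: RET status satisfies section 4.2, so the patient can re-enter if the other criteria hold. Data after withdrawal become available and the label becomes retrospective.
- RET-positive, withdrawn: RET status fails section 4.2. There is no re-entry route, and the stop rule applies.
- Entry into a clinical trial shows the difference clearly. It is a withdrawal reason for prospective patients, but that reason and exclusion criterion E 01 are both waived for retrospective patients. A RET-negative patient who enters a trial can be withdrawn and brought back. A RET-positive patient cannot.

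**Size of one move.** The amendment rationale gives 26 RET-positive and 8 RET-negative patients enrolled as of 02 Aug 2018. One reclassification is 1/8 = 12.5% of the prospective RET-negative cohort.

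**Effect on the columns (illustration).** Assumed, not in the documents: 3 responders among the 8 prospective RET-negative patients, 5 responders among 14 retrospective patients, and w withdrawn non-responders relabelled.

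| w | Prospective ORR | Retrospective ORR | Gap (points) | Pooled ORR |
|---|---|---|---|---|
| 0 | 3/8 = 37.5% | 5/14 = 35.7% | 1.8 | 8/22 = 36.4% |
| 1 | 3/7 = 42.9% | 5/15 = 33.3% | 9.5 | 8/22 = 36.4% |
| 2 | 3/6 = 50.0% | 5/16 = 31.2% | 18.8 | 8/22 = 36.4% |
| 3 | 3/5 = 60.0% | 5/17 = 29.4% | 30.6 | 8/22 = 36.4% |

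The pooled column is constant because a relabelled patient stays within the RET-negative total. The gap between source columns, which is what the comparability check looks at, can open through labelling alone.

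**Effect on the RET contrast (illustration).** For PFS, a RET-positive patient contributes follow-up only to withdrawal, while a RET-negative patient who re-enters can contribute later time and a later event. The direction of any bias cannot be fixed from the documents. For response, section 13.3 leaves patients with missing data out of percentages. Assume 14 responders among the 26 RET-positive patients, and 1 to 5 withdrawn patients with no response assessment who drop out of the denominator. ORR then goes from 14/26 = 53.8% to between 14/25 = 56.0% and 14/21 = 66.7%. A RET-negative patient in the same position could be recovered from the chart and kept in the denominator.

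**Internal consistency.** Three passages do not fit together:

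- The stop on data collection in 5.2 has no stated exception, yet the following paragraph collects more data.
- The adverse-event example in 5.2 is not among the reasons in 5.1, which also excludes stopping treatment as a reason.
- Voluntary withdrawal is a listed reason, and 5.2 does not exempt it from re-entry.

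**The case against.** Much of the case on the other side stands.

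- A reader might infer that the rule clears treatment failures out of the prospective cohort. The text does not support that. Non-response and progression are not withdrawal reasons, and a patient who stops treatment stays in the study by default. The adverse-event example is one poorly fitting illustration.
- A reader might also infer that relabelling biases the main RET-negative response estimate. It does not: the pooled figure is the same under either label. The harm from the label is confined to descriptive columns, on which section 13.3 sets no test and no pooling threshold.
- The rule has a legitimate use. A patient already on vandetanib fails prospective exclusion E 02, which does not apply retrospectively, and classing that patient as retrospective is correct. The same holds for incorrect enrolments that meet the retrospective criteria.
- The restriction to RET-negative patients comes from the accepted amendment plan, not from 5.2. Withdrawn RET-positive patients keep their data up to withdrawal.
- The second paragraph of 5.2 can be read as an exception to the stop rule, with visits ending and chart abstraction continuing. That reading is workable, but the protocol does not state it.
- Section 5.2 does not say that voluntary withdrawals are re-entered. It is silent, and the gap is a missing exemption.

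What the objection does not remove is the relabelling of correctly enrolled patients after a post-enrolment event, and the one-sided recovery of later data.

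**Conclusion.** The point holds in a limited form. Section 5.2 makes the analysis cohort of a validly enrolled patient depend on later withdrawal, and together with section 4.2 it allows data after withdrawal to be recovered in one RET group only. The affected results are the prospective and retrospective RET-negative columns and the RET contrast, chiefly PFS under objective F. The label leaves the pooled RET-negative response rate unchanged.

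The only size fixed by the documents is 12.5% of the prospective RET-negative cohort per patient moved, taking the 8 enrolled by 02 Aug 2018; a larger final cohort would make this smaller. All response rates in the illustrations rest on assumed responder and withdrawal counts. They show sensitivity in a very small cohort and do not demonstrate a bias. The RET-positive illustration also assumes that the missing-data rule is applied to ORR as written.

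The inconsistencies within 5.2 and with 5.1, and the silence on voluntary withdrawals, follow from the text alone.

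**What to change.** Revise section 5.2 as follows.

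- A patient validly enrolled prospectively is analysed in the prospective cohort. Any chart data dated after withdrawal are flagged.
- Reclassification as retrospective is limited to patients never included prospectively, or found to be incorrectly enrolled, who meet the retrospective criteria. Entry of patients found by database search under section 7.1 is unchanged.
- The sentence stopping data collection is amended to match, stating which data may still be abstracted and for whom.
- Nothing dated after the withdrawal date is collected for a patient who withdrew voluntarily.
- In the main RET comparison both groups are censored at withdrawal. Recovered RET-negative data are used in a sensitivity analysis.
- The adverse-event example is reconciled with the reasons in section 5.1.

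The cost is a short rewrite of section 5.2, a cohort flag in the database and one sensitivity analysis. The downside is that a few RET-negative patients contribute shorter follow-up to the main comparison.

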## 6 THERAPEUTIC STRATEGY

### 6.1 THERAPEUTIC STRATEGY OF A NON-INTERVENTIONAL STUDY

The assignment of a patient to a particular therapeutic strategy is not decided in advance by the protocol but falls within current practice. Therefore, the Sponsor will not reimburse vandetanib or any other medication, or any intervention or related expenses (due to the Non-Interventional nature of this study, only the laboratory analyses on biopsy samples already available can be reimbursed).

- Trade name and generic name: Caprelsa, vandetanib
- Dosage, form and strength: 300 mg/once daily, film-coated tablets

For prospective patients, doses and treatment regimens of vandetanib 300 mg, and other treatments for MTC, and concomitant medication should be or should have been prescribed according to the instructions in the SmPC (see [Appendix B](#)) and current practice.

In any case, all data available in the patient charts will be reported and described into the eCRF for the retrospective patients, even if not prescribed according to the SmPC.

There is limited data with 300 mg in patients with moderate renal impairment. The starting dose could be reduced to 200 mg in prospectively recruited patients with moderate renal impairment; safety and efficacy have however not been established with 200 mg.

All patients will be followed on treatment for at least 14 months provided it is considered appropriate for a patient to remain on treatment in the opinion of the Investigator. In any case, all included patients (prospective and retrospective) will be followed until death, loss of follow-up, or end of the study.

## 7 STUDY CONDUCT

### 7.1 PATIENT ENROLLMENT

For prospective patients, once vandetanib is launched in the country and the participant site has the appropriate local approvals, the Investigator will systematically identify and invite to participate in the study every patient who fulfills all the study inclusion criteria and none of the exclusion criteria.

The Principal Investigator will:

1. Obtain signed informed consent from the potential patient (except for retrospective patients).
2. Perform the RET determination in those patients where it is needed to confirm eligibility for prospective patients, provided that a biopsy sample is available and provided that no intervention is needed that would not have been done otherwise to obtain this sample. Verify the RET mutation negative status for retrospective patients.
3. Register the patient in the Web-based Data Capture (WBDC) system when the patient is entered into screening and/or is enrolled.

The recruitment of patients will be centrally controlled by the study team through the WBDC system. Therefore, in order to achieve the appropriate study sample target, it is of great importance that the Investigator registers in the study WBDC system, **immediately after known**, the information related to eligibility of the patient, even if some of these information are incomplete in the beginning.

All the prospective patients who sign the consent form will be allocated an E-code by the WBDC system. For patients who enter into screening period, but are not finally eligible, they will be registered in the WBDC as screening failure and withdrawn. All the screened patients will be registered in the site screening log and reason for withdrawal documented.

Applicable for retrospective patients: the site will search the databases for the prevalent MTC patients and review the records to consider recruitment using 2010 as a cutoff without any limitation for the date of diagnosis and identify among these patients all those who were RET mutation negative, all of whom should be included into the study (unless if there is a contract with another company for a clinical trial that precludes this).

For the cases where the RET test needs to be done on an available biopsy sample to confirm eligibility for the study, without any intervention that would not have been done otherwise, a signed informed consent should be always obtained prior to performing the laboratory analyses on the available sample (except for retrospective patients). An informed consent is never needed for the intervention itself, since this intervention should never be related to the study.

The Sponsor will reimburse the costs associated to the RET determination when the test is solely performed to confirm eligibility for the study, provided that the intervention allowing to collect the sample (biopsy) was not done specifically for the study.

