**Table 4 - Study plan**

Time	Screening/Enrollment visit or baseline time point	Follow-up visits for prospective patients or follow-up time points for retrospective patients
Obtain Informed Consent a	X	-
Inclusion/exclusion criteria assessment	X	-
Patient Characteristics, including RET status b	X	-
Disease assessment c	X	X
Treatment information	X	X
Safety information	X	X
Laboratory d	X	X

*a* Waiver for retrospective patients

*b* For retrospective patients: RET mutation negative status may have been performed before or after start of the treatment of medullary thyroid cancer (MTC) (Vandetanib or another treatment).

*c* Disease assessment should be consistent (same time frequency and method) within a site across the study for prospective patients, but not necessarily for retrospective patients.

*d* Potassium, creatinine, calcium, magnesium and thyroid stimulating hormone (TSH) will be collected at baseline, at 1, 3, 6 and 12 weeks after starting treatment and every 3 months for one year.

RET= Rearranged during transfection

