#### 4.3 EXCLUSION CRITERIA

- E 01. Current or planned inclusion/participation in a clinical trial, not applicable for retrospective patients.
- E 02. Patients already receiving vandetanib or who have received vandetanib for their MTC before the study first visit, not applicable for retrospective patients.
- E 03. Contraindications according to the vandetanib SmPC, not applicable for retrospective patients and for patients who do not receive vandetanib:
- A) Patients with a QTc interval over 480 msec:
    - Congenital long QT syndrome
    - Concomitant use of vandetanib with the following medicinal products known to also prolong the QT interval and/or induce Torsades de pointes: Arsenic, cisapride, erythromycin intravenous, toremifene, mizolastine, moxifloxacin, Class IA and III antiarrhythmics
  - A) Currently pregnant or breast-feeding, not applicable for retrospective patients.
  - B) Hypersensitivity to the active substance or to any of the excipients, not applicable for patients who do not receive vandetanib.
  - C) Severe renal impairment: creatinine clearance <30 mL/minute calculated by Cockcroft-Gault formula, not applicable for patients who do not receive vandetanib (See [Appendix D](#)).
  - D) Serum bilirubin greater than  $1.5 \times$  the upper limit of reference range (ULRR), not applicable for patients who do not receive vandetanib.
  - E) Potassium, magnesium or calcium outside the normal laboratory range, not applicable for patients who do not receive vandetanib.

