#### **Retrospective patients:**

Patient confidentiality will be strictly maintained. Access to the WBDC system will be controlled via a hierarchical user-name and password control. Patient data will be pseudonymized through design of data entry fields that do not permit the entry of identifying information such as initials, date of birth, or center-assigned patient identifiers. Only trained site staff will enter data into the eCRFs. Patient's ages in range of 5 years, but not date of birth, will be entered. Patient identifiers used by sites will not be entered; rather the WBDC program will automatically assign a study ID to each patient. The pseudonymized data as entered into the WBDC system will be visible to the Clinical Research Organization (CRO) and the Sponsor, but only center staff will be able to trace a study ID number back to a patient identity, a necessary measure to allow center staff to respond to data queries raised by the CRO later. Eventually, once the database will be frozen, the sites will destroy this correspondence between study ID and their own identifiers.

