### 13.3 STATISTICAL ANALYSIS

The changes implemented in the protocol amendment define, in addition to the original study population, 2 other groups of patients: a retrospective group and a group of patients from the Study DC4200C00058 whose RET data were re-analyzed with new classifications as positive and negative. The criteria for selecting these data, described elsewhere in this amended protocol, are intended to assure that the populations are comparable, and hence, may be pooled. In order to confirm comparability, all analyses will report the descriptive statistics for each of these groups as well as the pooled data both for RET mutation positive and RET mutation negative subjects, as presented in [Table 2](#).

Table content will adapt to the type of variable as defined below:

Qualitative variables will be described by number of observed values, percentage and number of missing values (patients with missing data will not be included in the percentage calculation).

Quantitative variables will be described by number of observed values, mean, standard deviation, median, first quartile, third quartile, minimum and maximum.

For time-to-event, the median time to event and, number and percentage of each group remaining at risk at the last point of observation will be provided.

Statistical analyses will be conducted with SAS Software version 9.3 or upper.

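### The retrospective search neither excludes nor flags participants of Study D4200C00058, so a RET-negative patient could enter the pooled column twice

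*Protocol*

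**What the plan says.** **Enrolment.** For retrospective patients, Section 7.1 has each site search its records with 2010 as a cutoff and no limit on diagnosis date, and "identify among these patients all those who were RET mutation negative, all of whom should be included into the study". The one exception is "unless if there is a contract with another company for a clinical trial that precludes this".

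**Exclusions.** Section 4.3 lifts E 01 ("Current or planned inclusion/participation in a clinical trial, not applicable for retrospective patients") and E 02 ("Patients already receiving vandetanib or who have received vandetanib for their MTC before the study first visit, not applicable for retrospective patients"). The Synopsis (Target patient population) admits retrospective RET-negative patients treated with vandetanib at any time.

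**RET timing.** On the retrospective arm, Section 4.2 says that "RET mutation negative mutation status could have been determined within 18 months before or after start of treatment (with vandetanib or another drug"). Table 4, footnote b, says only that "RET mutation negative status may have been performed before or after start of the treatment of medullary thyroid cancer". The overall rationale for the amendment also describes a determination independent of the start of vandetanib.

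**Pooling.** Section 13.3 adds to the original population "a retrospective group and a group of patients from the Study DC4200C00058 whose RET data were re-analyzed". Table 2 has a column for each source and an *All* column within each RET status.

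**Identity.** Under Section 10.3, a retrospective patient receives a new study ID, age is entered in 5-year ranges, and initials, date of birth and site identifiers are barred. Only site staff can trace the ID to a person. Once the database is frozen, "the sites will destroy this correspondence between study ID and their own identifiers".

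**The concern.** The retrospective arm and the Study D4200C00058 group are treated as separate sets of people, but the enrolment rule does not keep them apart. The protocol foresees one kind of re-entry: under Section 5.2 a prospective patient moved to the retrospective collection keeps the same ID. It has no counterpart for a person who already has a record in Study D4200C00058.

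A person present in both sources would appear once in each source column, which is harmless, and twice in the pooled RET-negative column. That would overstate the number of patients, weight that person's outcome twice, and make any interval computed on the record count too narrow. The risk lies only in the RET-negative group, because no RET-positive patient enters retrospectively. That group is the subject of the specific obligation (Appendix B, Annex II, part E).

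**Working it through.** **1. Is the route open?**

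- Participation in Study D4200C00058 does not exclude a retrospective patient (E 01 waived), nor does vandetanib received in it (E 02 waived).
- The exception in Section 7.1 concerns another company's contract. It does not remove duplicates.
- If the 18-month window in Section 4.2 governs, a patient classed negative only by the later re-analysis would not clearly qualify. The results of Study D4200C00058 are cited from 2010, and the re-analysis belongs to a plan accepted on 28 February 2019. If Table 4, footnote b, governs, there is no such barrier.
- On original testing the route stays open under either text, provided the test date fits. Section 1.1 says that Study D4200C00058 called a tumour negative only if all 7 assays succeeded. Section 3.2 does not require every exon to have been tested successfully. Appendix B (SmPC section 5.1) describes 79 patients without M918T and with no other mutation found, 71 of them with incomplete sequencing. Some could meet Section 3.2 on their original result while counting as unknown in Study D4200C00058, and so fall in the group to be re-analysed. The assay dates are not given.

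**2. Reproduce the plan's figure.** Table 1 follows from p ± 1.96 × SD/√n with p = 0.35 and SD = 0.4770, where √(0.35 × 0.65) = 0.4770.

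- n = 20: half-width 20.9 points, 14.1% to 55.9%
- n = 25: half-width 18.7 points, 16.3% to 53.7%
- n = 30: half-width 17.1 points, 17.9% to 52.1%

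All three agree with the protocol.

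**3. Effect of duplicates on precision.** Let N be the pooled records and d the people who appear twice with the same outcome. Then d people have weight 2 and N − 2d have weight 1, so the squared weights sum to 4d + (N − 2d) = N + 2d. Hence Var = p(1 − p)(N + 2d)/N², and the effective n is N²/(N + 2d). The values of d are assumptions. For N = 25 and p = 0.35:

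| d | distinct people | effective n | half-width (points) | coverage of the nominal 95% interval |
|---|---|---|---|---|
| 0 | 25 | 25.0 | 18.7 | 95.0% |
| 2 | 23 | 625/29 = 21.6 | 20.1 | 93.1% |
| 5 | 20 | 625/35 = 17.9 | 22.1 | 90.2% |
| 8 | 17 | 625/41 = 15.2 | 23.9 | 87.4% |

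If the 25 records with d = 5 are de-duplicated, 20 people remain and the half-width is 20.9 points. That is less than 22.1, because unequal weighting itself costs precision.

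**4. Effect on the estimate.** Take 20 distinct people with 7 responders (35.0%). Counting 2 non-responders twice gives 7/22 = 31.8%; counting 2 responders twice gives 9/22 = 40.9%.

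**5. Can duplicates be found?** Before the freeze they can, because site staff hold the key and answer queries. Afterwards the key is gone. Section 12.1 places the analysis after clean file, so a duplicate first suspected at analysis may have to be matched on the diagnosis, assay and treatment dates collected under Section 8.2. It could not then be confirmed through the key.

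**The case against.** Several points count against a stronger reading.

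- **A reader might infer that patients are in fact counted twice.** The documents do not show it. Overlap of sites or patients is nowhere stated. Sites look for patients recorded as negative, whereas the re-analysis is aimed at patients whose status was unknown. With the 18-month window, most of them may stay out. This stands, and it is why d may be zero.
- **A reader might take the 8 RET-negative patients in Section 1.1 as the size of the problem.** They had already been classified, so they are not clearly in the re-analysed group. A patient who is only in the retrospective group gives one record, not two.
- **A reader might infer that duplicates could never be found.** Sites can trace patients until the freeze, and the collected dates allow an indirect match later.
- **Table 1 is a planning table for patients enrolled in this study.** The protocol does not specify an interval for the pooled response rate in treated patients, and each source is reported separately. This stands, so the half-widths above are illustrations.
- **A merging rule may sit in the SAP or the data management plan, neither of which is shown.** That is fair for the rule itself. But the eligibility text is the protocol's own, and a later rule works best if participation was recorded while the sites still held the key.

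**Conclusion.** The gap is real but limited. As written, Sections 7.1 and 4.3 let a participant of Study D4200C00058 enter retrospectively, and Section 13.3 can then place both records in one pooled column. The documents support a possibility of double counting, not an occurrence.

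For 25 pooled records at 35%, the half-width would be understated by 1.4 points (20.1 − 18.7) with d = 2, 3.4 points with d = 5 and 5.2 points with d = 8. With d = 0 nothing changes. These figures assume that an interval is computed on the record count and that both records of a person show the same outcome. The second assumption may fail: response in Study D4200C00058 came from central blinded review (Appendix B), while Appendix C here describes assessment by the investigator.

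Separately, Section 4.2 and Table 4 disagree on the RET window, and that disagreement determines how wide the route is.

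**What to change.** 1. Add one yes/no eCRF item for retrospective patients, asking whether the patient took part in Study D4200C00058, answered by the site before the freeze.
2. State in advance which source supplies the record when a person is in both, and count each person once in every pooled column. The separate source columns can stay as they are. A yes does not by itself show that the person's Study D4200C00058 record is in the pooled group, so settle this by site query while the key exists.
3. Report the number of overlaps, including zero.
4. Reconcile the RET timing in Section 4.2 with Table 4, footnote b, and with the amendment rationale.

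The cost is one data item, a de-duplication step before lock and a sentence in the analysis text. The downside is that the pooled RET-negative count may fall slightly.
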